## **10. MONITORING**

### **10.1 RISK ASSESSMENT**

This is considered a low risk study.

All the drugs being used are being prescribed for routine indications and have well established safety profiles. As such only passive monitoring for adverse events will be undertaken during the study.

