#### Duration

The duration of the study is 12 months. For all participants, there will be a 15 day on-study period which will include two visits by the study team

- Day 1 for baseline medical assessment and delivery of azithromycin/tetracycline and ivermectin/permethrin
- Day 8-15 for delivery of second dose of ivermectin/permethrin

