## 6. TRIAL MEDICATION

### 6.1 Name and description of investigational medicinal product(s)

#### Azithromycin

Azithromycin is an azalide antibiotic, a subclass of the macrolides. After oral administration, peak plasma concentration is reached in 2 to 3 hours. Tissue levels of azithromycin are greater than plasma levels (up to 50 times the maximum plasma concentration). Biotransformation occurs mainly in the liver, with elimination mainly by the bile and partly by urine. The plasma terminal half-life is 2-4 days. Azithromycin is indicated for mild to moderate infections such as respiratory-tract infections, otitis media, skin and soft-tissue infections and genital chlamydial infections. Azithromycin is the treatment of choice for mass treatment of both yaws and trachoma. The recommended dose for the mass treatment of yaws is a single-dose of azithromycin 30mg/kg up to a maximum of 2g. Azithromycin is available as 250 mg or 500 mg tablets and as oral suspension.

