#### Ivermectin

Ivermectin is an anthelmintic. Ivermectin is metabolized in the liver, and ivermectin and/or its metabolites are excreted almost exclusively in the feces over an estimated 12 days, with less than 1% of the administered dose excreted in the urine. After oral administration, the apparent plasma half-life of ivermectin is approximately 16 hours. Ivermectin is indicated for the treatment of onchocerciasis or river blindness caused by *Onchocerca volvulus* and for strongyloidiasis caused by *Strongyloides stercoralis*. The recommended dosage for treatment of scabies is two oral doses designed to provide approximately 200µg of ivermectin per kg of body weight. The same dose is recommended in the Solomon Islands. Ivermectin is available in 3mg tablets.

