## 7. SAFETY REPORTING FOR DRUG TRIALS

### 7.1 DEFINITIONS

Term	Definition
Adverse Event (AE)	
Any untoward medical occurrence in a participant to whom a medicinal product has been administered, including occurrences which are not necessarily caused by or related to that product.
 
An AE can therefore be any unfavourable and unintended sign (including an abnormal laboratory finding), symptom, or disease temporally associated with the use of an investigational medicinal product (IMP), whether or not considered related to the IMP.

Adverse Reaction (AR)	
Any untoward and unintended response in a participant to an investigational medicinal product which is related to any dose administered to that participant.
 
The phrase “response to an investigational medicinal product” means that a causal relationship between a trial medication and an AE is at least a reasonable possibility, i.e. the relationship cannot be ruled out.
 
All cases judged by either the reporting medically qualified professional or the Sponsor as having a reasonable suspected causal relationship to the trial medication qualify as adverse reactions.

Serious Adverse Event (SAE)	
A serious adverse event is any untoward medical occurrence that:
 
 
• Results in death
 
• Is life-threatening
 
• Requires inpatient hospitalisation or prolongation of existing hospitalisation
 
• Results in persistent or significant disability/incapacity
 
• Consists of a congenital anomaly or birth defect
 
 
Other ‘important medical events’ may also be considered serious if they jeopardise the participant or require an intervention to prevent one of the above consequences.

Serious Adverse Reaction (SAR)	
An adverse event that is both serious and, in the opinion of the reporting investigator, believed with reasonable probability to be due to one of the trial treatments, based on the information provided.

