#### 7.3.1 Non serious Adverse Reactions (ARs)/Adverse Events (AEs)

Given the established safety profile of the drugs being used in this study and the fact that they are being used for established indications we will only collect data on SAEs and SUSARs.

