#### 7.3.2 Serious Adverse Reactions (SARs)/Serious Adverse Events (SAEs)

Serious Adverse Events (SAEs) and Serious Adverse Reactions (SARs) should be reported to the study coordination centre within 24 hours of the local site being made aware of the event.

An SAE form should be completed and submitted to the study coordination centre with as much detail of the event that is available at that time. If awaiting further details, a follow up SAE report should be submitted promptly upon receipt of any outstanding information. The CI (for a single-centre trial) or PI (for a multi-centre trial) must record the event with an assessment of seriousness, causality and expectedness.

Any events relating to a pre-existing condition or any planned hospitalisations for elective treatment of a pre-existing condition do not need reporting as SAEs.

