### Interim Visit

At Month 3 an interim visit will be made. Individuals will be re-examined and swabs collected from those with clinical evidence of impetigo. Data from previous studies indicates that scabies and impetigo continue to decline between month 3 to month 12 following community mass treatment for scabies therefore treatment will not routinely be offered at this time point.

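### SAE detection is passive only: no planned visit asks about death, hospital admission or birth outcome, so a report of no SAEs could not be told apart from not having asked

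*Combined protocol and SAP*

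**What the plan says.** Section 7.3.1 drops non-serious events: "we will only collect data on SAEs and SUSARs". Section 10.1 then sets how events come to light: "As such only passive monitoring for adverse events will be undertaken during the study". The reason given is that the drugs have known safety profiles and are used for routine indications.

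Under Section 7.3.2, SAEs go to the coordination centre "within 24 hours of the local site being made aware of the event". Neither Section 7.3 nor any other section gives a start or end date for SAE collection.

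The SAE definition in Section 7.1 lists death, life-threatening events, hospitalisation and lasting disability, and also an event that "Consists of a congenital anomaly or birth defect". Section 6.9 confirms that pregnant women take part, with permethrin in place of ivermectin.

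Section 8 describes further contacts after Day 1: a visit for the second scabies dose, an interim visit ("At Month 3 an interim visit will be made. Individuals will be re-examined") and a month-12 follow-up of all individuals. Section 12 states that there will be no DSMB.

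**The concern.** When a trial records only serious events, its safety statement is only as good as its means of finding them. Here the only route is that someone tells the site. A participant who died, or was admitted to another hospital, would simply not be present at the next visit, and nothing in the visit descriptions prompts the team to ask why. A birth defect counts as an SAE, but no described visit asks about births, although a pregnancy under way at Day 1 would normally have ended before month 12.

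What is at stake is how a low or zero SAE count is read. Section 3.2 cites the absence of SAEs in an earlier study as support for the safety of co-administration. This trial's count could be cited in the same way, and a reader could not tell whether there were no events or whether nobody asked.

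**Working it through.** **1. What each contact collects (Section 8)**

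| Contact | Described content | Enquiry about death, admission or birth |
|---|---|---|
| Day 1 | Skin examination, finger-prick blood, lesion swabs, weighing, observed treatment | Not applicable (baseline) |
| Second scabies dose | Second dose offered | None |
| Month 3 | Re-examination, swabs if impetigo | None |
| Month 12 | Skin examination, finger-prick blood, lesion swabs; azithromycin offered in the sequential arm | None |

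Set beside Section 10.1, this is consistent: passive-only detection means no routine question. It is a declared choice, not a contradiction.

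**2. Time between contacts**

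Section 3 (Duration and the two arm descriptions) puts the second scabies dose on Day 8 to 15. Section 8 and Section 10.3 put it on Day 8. Taking month 3 as Day 90 (assumption):

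- Gap to the next contact: 90 − 15 = 75 days to 90 − 8 = 82 days.

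Section 10.3 does not list a month-3 visit. If none is held, and month 12 is taken as Day 365 (assumption):

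- Gap: 365 − 15 = 350 days to 365 − 8 = 357 days.

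Throughout these gaps, an SAE is recorded only if word of it reaches the site.

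**3. What a zero count would mean**

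Inputs: n = 637 per arm (Study Summary), or 2 × 637 = 1,274 in both arms. Capture fraction s: not in the documents, so a range is assumed.

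Formula: one-sided 95% upper limit on the true SAE rate with no reported event = (1 − 0.05^(1/n)) / s.

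| n | s = 1 | s = 0.5 | s = 0.25 |
|---|---|---|---|
| 637 | 0.47% | 0.94% | 1.88% |
| 1,274 | 0.23% | 0.47% | 0.94% |

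The limit scales with 1/s, and the trial as described would yield no information on s. The formula treats people as independent and ignores clustering by community, so it is an illustration only.

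**4. Two figures that are not counts of missed SAEs**

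- Section 9 allows 10% loss to follow-up: 0.10 × 637 ≈ 64 per arm. This is a planning allowance. The protocol does not say how a death would be classified.
- If 1.5% to 3% of 1,274 residents were pregnant at Day 1 (assumption, not in the documents), that is 1,274 × 0.015 ≈ 19 to 1,274 × 0.03 ≈ 38 pregnancies. Only the parallel arm is offered azithromycin on Day 1, so with equal arms about half of them, roughly 10 to 19, would be exposed to it.

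**The case against.** **The choice is deliberate.** The drugs are given for standard indications. Section 6.7 cites a co-administration study of more than 3,000 people with no serious events, and Section 3.2 cites a further study with none. Safety is not a primary or secondary outcome. This stands, and it supports the decision not to collect non-serious events. It does not explain why teams who are already in the community should not ask about serious ones.

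**Some events will reach the site anyway.** The communities lie in the catchment of the hospital whose staff take part in the study, so local admissions may be noticed. That is a fair inference, but it does not cover deaths or admissions elsewhere. The record forms and information sheet are listed as appendices and are not reproduced. A question could sit there, although Section 10.1 as worded would rule out a routine one.

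**A stronger reading that does not hold.** Section 3 says "For all participants, there will be a 15 day on-study period which will include two visits by the study team", and the second dose may fall on Day 15. A reader might infer that safety follow-up closes on the day of that dose, and set this against ivermectin being "excreted almost exclusively in the feces over an estimated 12 days" and the statement on azithromycin that "The plasma terminal half-life is 2-4 days". The documents do not support this:

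- No section makes the 15-day period the SAE window.
- Section 10.1 ties monitoring to the study, which Section 3 says lasts 12 months, and Section 7.3.2 has no cut-off. An SAE that the site learns of on Day 20 is reportable as written.
- The Day-15 dose arises only under the Section 3 timing. Section 8 and Section 10.3 give Day 8.
- Pregnant women and the smallest children receive permethrin, so ivermectin excretion times do not apply to them.

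**Month 3.** Nor can one say that every participant is seen then. The Interim Visit text refers only to individuals, and Section 10.3 omits the visit.

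**Conclusion.** The point holds as a low-cost improvement to a stated design choice, not as an error or an internal contradiction. SAEs are the only safety events kept, they are found only by chance notification, and no described visit asks about the outcomes that define them. The absence of a stated SAE window adds to this, but on its own it would be no more than missing detail.

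The size cannot be given as a number of missed events. It can be shown as a loss of meaning: the upper limit implied by a zero count in 637 people moves from 0.47% to 0.94% or 1.88% if capture is one half or one quarter, and those capture rates are assumed. The conclusion also assumes that the appendix forms contain no serious-event question. Sample size and the primary outcome are not affected.

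**What to change.** 1. **Section 10.1.** Keep passive reporting, and keep the decision not to collect non-serious events. Add one fixed question at contacts already planned: the second scabies-dose visit, month 3 if held, and month 12. It should cover death, hospital admission and, for women pregnant at Day 1, birth outcome. For absentees, ask household members who are present.
2. **Section 7.3.** State that SAE reporting covers the whole study and is not limited to the 15-day on-study period. Word the end of reporting so that it does not cut off events after the azithromycin offered to the sequential arm at month 12, since Section 8.2 closes the trial at the end of that period.
3. **Reconcile the visit schedule.** The second-dose timing differs between Section 3 and Sections 8 and 10.3. The month-3 visit appears in Section 8 but not in Section 10.3.

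**Cost.** A few lines on the record forms, a short question per person, some proxy enquiry for absentees, and additional SAE forms with causality assessment for background deaths and admissions. Section 7.3.2 already exempts events relating to pre-existing conditions and planned admissions for them, which limits the number of forms. No new visits are needed. If the change is classed as a substantial amendment, Section 11.1 requires a favourable opinion from both ethics committees first.

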### **10.2 MONITORING AT STUDY COORDINATION CENTRE**

Data will be entered directly into an electronic database at the time of the study.

### **10.3 MONITORING AT LOCAL SITE**

Site visits will take place at D1 (treatment for yaws and scabies), D8 (second treatment for scabies) and month 12 (assessment of outcome).

## **11. REGULATORY ISSUES**

### **11.1 ETHICS APPROVAL**

The Study Coordination Centre has obtained approval from the LSHTM Research Ethics Committee, as well as the [Atofi Adventist Hospital Ethics Committee](#).

Substantial protocol amendments will not be implemented until a favourable opinion has been granted from both the LSHTM and AAH ethics committee.

Correspondence from both ethics committees will be maintained in the trial master file.

As the duration of the study is 1 year the annual progress report will accompany the notification of the end of the study.

### **11.2 CONSENT**

Prior to the study commencing a research training workshop will be held at AAH and which will be attended by AAH and other study staff as well as key community leaders. This meeting will provide an opportunity for explanation of the study aims and methodologies and for study staff to answer questions about the study design and implementation.

Prior to performing any study specific procedure, written informed consent will be obtained for each subject. Information sheets explaining the study will be distributed to community nurses who will be trained in explaining the study. These information sheets will also be available to study participants. For subjects below the legal age, a parent or legal guardian must provide consent. Written consent will be obtained in local dialect on all occasions.

### **11.4 CONFIDENTIALITY**

Subject confidentiality is strictly held in trust by the participating investigators, research staff, and the sponsoring institution and their agents. This confidentiality is extended to cover testing of biological samples and the clinical information relating to participating subjects. The study protocol, documentation, data and all other information generated will be held in strict confidence. No information concerning the study or the data will be released to any unauthorized third party, without prior written approval of the sponsoring institution. Authorized representatives of the sponsoring institution may inspect all documents and records required to be maintained by the Investigator, including but not limited to, medical records (office, clinic or hospital) and pharmacy records for the subjects in this study. The clinical study site will permit access to such records. All evaluation forms, reports and other records that leave the site will be identified only by the Subject Identification Number (SID) to maintain subject confidentiality. Clinical information will not be released without written permission of the subject, except as necessary for monitoring by HREC or regulatory agencies.

**11.5 INDEMNITY**

London School of Hygiene & Tropical Medicine holds Public Liability ("negligent harm") and Clinical Trial ("non-negligent harm") insurance policies which apply to this trial.

**11.6 SPONSOR**

London School of Hygiene & Tropical Medicine will act as the main sponsor for this study. Delegated responsibilities will be assigned locally.

**11.7 FUNDING**

This study is funded as part of a Wellcome Trust Research Fellowship held by [name]. No payments will be made to patients participating in this study.

**11.8 AUDITS AND INSPECTIONS**

The study may be subject audit by the London School of Hygiene & Tropical Medicine under their remit as sponsor, the Study Coordination Centre and other regulatory bodies to ensure adherence to GCP.

## **12. TRIAL MANAGEMENT**

A Trial Management Group (TMG) will be appointed and will be responsible for overseeing the progress of the trial. The day-to-day management of the trial will be co-ordinated by [name] and [name].

All treatments in the study are being given for standard indications and the drugs have known safety profiles including in the setting of co-administration. A DSMB will therefore not be appointed.

All data will be held jointly by LSHTM and AAH. Data will be stored on an encrypted password protected server at both LSHTM and AAH.

### **13. PUBLICATION POLICY**

All publications and presentations relating to the study will be authorised by the Trial Management Group. The first publication of the trial results will be in the name of the Trial Management Group, if this does not conflict with the journal's policy. If there are named authors, these will include at least the trial's Chief Investigator, Statistician and Trial Coordinator. Members of the TMG and the Data Monitoring Committee will be listed and contributors will be cited by name if published in a journal where this does not conflict with the journal's policy. Authorship of parallel studies initiated outside of the Trial Management Group will be according to the individuals involved in the project but must acknowledge the contribution of the Trial Management Group and the Study Coordination Centre.

## **APPENDICES**

1. Informed Consent Form
2. Assent Form
3. Study Information Sheet
4. MDA Record Form
5. Skin Examination Record Form
6. SAE Report Form
7. Summary of Product Characteristics for Azithromycin
8. Summary of Product Characteristics for Ivermectin
9. Summary of Product Characteristics for Permethrin
